High-Definition Transcranial Direct Current Stimulation (HD-tDCS) in logopenic variant Primary Progressive Aphasia (lvPPA): Effects on Language and Neural Mechanisms.

Principal Investigator: [name] (Department of Neurology).

Co-investigator: [name] (Department of Neurology)
[name] (Department of Neurology)
[name] (Department of Neurology)
[name] (Department of Neurology)

Address

Medical College of Wisconsin
[name]
[name]

Funding Sponsor: Neurosciences Research Center.

Version: 5

Version Date: May 26, 2022

PROTOCOL SUMMARY

Title	High-Definition Transcranial Direct Current Stimulation (HD-tDCS) in logopenic variant Primary Progressive Aphasia (lvPPA): Effects on Language and Neural Mechanisms.
Principal Investigator	[name]
Study Site	Medical College of Wisconsin
Device Trial Phase	Pilot Study
Study Disease	logopenic variant Primary Progressive Aphasia (lvPPA)
Main Eligibility Criteria	
 • Clinical lvPPA or imaging-supported lvPPA • Age 45 years and older • Structural brain MRI done within the 3 years prior to enrollment.
Study Rationale	
The logopenic variant of Primary Progressive Aphasia (lvPPA) is a neurodegenerative disorder often referred to as the 'language form' of Alzheimer's Disease (AD). The current conceptual disease framework assumes a relatively widespread neurodegeneration which causes patients to continue to use pre-existing, specific neural areas with declining efficiency.
 
tDCS is a non-invasive, painless brain stimulation technique that appears to enhance language production when delivered during language training. To date, studies utilizing tDCS in lvPPA patients have been limited to conventional montages that are not suitable for focal targeting of brain tissue. High-Definition tDCS (HD-tDCS) is a recently developed system that allows for more focal stimulation based on increased current focality and intensity, and the individualized modelling of the patient's brain tissue.
 
Considering this, use of HD-tDCS to target the most consistent neural correlate of lvPPA (the left posterior temporo-parietal cortex) should be explored.

Primary Objectives	Determine the efficacy of HD-tDCS for the improvement of language performance in lvPPA.
Secondary Objectives	(ii) evaluate the effects of HD-tDCS on functional connectivity using functional Magnetic Resonance Imaging (fMRI), and (iii) elucidate its effects on spontaneous neuronal oscillatory patterns using Magnetoencephalography (MEG).
Endpoints	
 • Primary outcome measurements: Language performance changes as assessed at baseline and after tDCS stimulation procedures (time frame: 2 weeks). • Secondary outcome measurements: (ii) Changes in brain functional connectivity as assessed at baseline and after tDCS stimulation (time frame: 2 weeks) (iii) Changes in abnormal patterns of neuronal frequencies and synchronizations as assessed at baseline and after tDCS stimulation procedures (time frame: 2 weeks).

Study Design	
This clinical utility study is a randomized, double-blind, sham-controlled trial in which stimulation or sham will be administered to 20 subjects over the age of 45 years, with the order of treatments counterbalanced in a within-subject crossover design. Stimulation and sham sessions last 20 minutes and occur for 10 days over a 2-week period.
 
The study consists of Pre-screening (Visit –1), Baseline (Visit 1), a 2-week Treatment Period (Visits 1-10), a 16-week Washout Period, an Interim Assessment (Visit 11), a second 2-week Treatment Period (Visits 12-21), and a Final Assessment (Visit 22).

Study Agent/ Intervention Description	tDCS and sham stimulation sessions lasting 20 minutes at a current intensity of up to 2mA in the targeted cortical tissue
Number of Subjects	20
Subject Participation Duration	28 weeks: 2 weeks of tDCS/sham, followed by a 16-week washout, followed by 2 weeks of tDCS/sham, followed by an 8-week final assessment.
Duration of Follow up	None
Estimated Time to Complete Enrollment	18 months
Statistical Methodology	The collection of pilot data from this study will provide initial estimates of the variability and the effect sizes. This information will then be used for the more formal calculations of power and sample size necessary to conduct a pivotal trial. All future statistical testing will use repeated measures ANOVA once a large enough sample is reached.
Safety Assessments	Data safety monitoring board meetings will be scheduled to monitor progression of the study and review drug adverse events
Efficacy Assessments	(i) Consent rate and treatment completion rate (ii) Statistically significant differences between baseline and post- tDCS stimulation performance on a series of language metrics.
Unique Aspects of this Study	This is the first study to evaluate the efficacy of HD-tDCS for the treatment of language deficits of lvPPA, a neurodegenerative and progressive condition with no known effective treatment. It would also be the first study to access whether HD-tDCS can increase brain functional connectivity and regulate abnormal patterns of neuronal frequencies and synchronizations in this patient population.

Table of Contents

1. Study Objectives	5
2. Background and Significance	6
3. Rationale	7
4. Study Design	8
5. Study Visits and Procedures	9
6. Data Management	15
7. Data Safety Monitoring Plan	16
8. References	21

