1.3. Outcome Measurements

The following outcome measurements will be used to test our proposed hypothesis:

- **Primary outcome measures:** Language performance as assessed at baseline and post-stimulation procedure (time frame: 2 weeks)
- **Secondary outcome measures:** Language network resting state changes after stimulation procedure (time frame: 2 weeks)
- **Tertiary outcome measures:** Resting-state neuronal frequencies and synchronizations changes after stimulation procedure (time frame: 2 weeks)

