‘Trained’ tasks. This includes items tested at baseline and after treatment periods, with half of them also practiced (i.e. trained) during all stimulation procedures (either sham or real tDCS). It will include the reading of words and non-words and the repetition of non-words (approximately 480 items, a total of 288 items for reading and 192 for repetition, divided across two treatment periods). Non-word tasks were selected due to their reliance on the kind of phonologic mechanisms subserved by the dominant temporo-parietal cortex and impaired in IvPPA (Pillay et al., 2017). We will test vocal reaction times and the data will be analyzed using a Matlab custom script. Estimated testing time: 25-30 minutes.

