6. DATA MANAGEMENT

6.1. A secure web-based system will be used to enroll patients and obtain the randomly assigned treatment group. Data forms will be printed, completed, and entered into the database using a secure web-based application. The database will be monitored for completeness, consistency, accuracy, and timeliness. No patient-identifying information will be stored in the database. To ensure that data are secure from external violation, computer systems containing study data will be password protected, and physical access to the computer systems will be limited.

6.2. Determination of changes in Language Function and Concurrent Improvement in Network Activity.

The language and MRI/rfMRI datasets will be obtained at baseline (before sham/active tDCS administration) and on the last day of each 2-week treatment period. These two time points will be denoted $t = 1, 2$. The two 10-

subject groups, both of which will receive both sham and active tDCS at different treatment phase, will be denoted $g = 1, 2$. The set of Language (LG) scores for subject s , from group g , at time t will be denoted $LG(s, g, t)$, where $s = 1, \dots, 10$; $g = 1, 2$; and $t = 1, 2$. The Language-Network functional connectivity (LFC) calculated between the left posterior temporal and inferior parietal cortex for subject s , from group g , at time t will be denoted $LFC(s, g, t)$.

6.3. Language Changes Due to Stimulation. Scores across all tests within the language battery will be combined into one composite measure to facilitate assessment of overall language performance across domains. All seven scores will be normalized to a Z-score by transforming individual raw test scores according to the mean and standard deviation of the scores for all subjects. Then, Z-scores of each test will be averaged to obtain an individual composite language Z-score (McConahey et al., 2017). We will employ age, years of education, gender, and gray matter (GM) volume as time-invariant covariates to obtain residual variables to determine the LG changes due to stimulation. We will model the LG score as a function of these nuisance regressors. This regression will be performed using all the data (i.e., all subjects, all groups, and all times):

$$\Delta LG(s, g, t) = \beta_0 + \beta_1 Age(s) + \beta_2 Edu(s) + \beta_3 GM(s) + \beta_4 Gender(s) + Res(s, g, t)$$

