Define $\widetilde{LG}(s, g, t) \equiv Res(s, g, t)$. We will test the residuals $\widetilde{LG}(s, g, t)$ using a *three-factor crossed-nested* ANOVA, with fixed factors *group* and *time*, and random factor *subject* nested within *group*. We will test for group and time main effects, as well as the group \times time interaction. If we find significant main effects or interactions, we will perform post hoc procedures to determine which time and group combinations are significantly different.

6.4. Functional-Connectivity Changes Due to Stimulation. We will use the well established Human Connectome Project (HCP) fMRI processing pipelines implemented by [name] group at MCW, which include state-of-the-art noise removal, spatial normalization, and surface-based cortical parcellation methods.

Functional connectivity matrices will be computed by first parcellating the brain into multiple regions of interest (ROI), averaging the preprocessed fMRI signal over each ROI, and then computing the Z-transformed correlation coefficient between every ROI pair. The functional connectivity of a number of different parcellation schemes will be examined. This includes anatomical atlas based parcellation, such as the Harvard Oxford atlas, a validated probabilistic atlas implemented in FSL that divides each hemisphere into 56 regions corresponding to portions of cortical gyri and subcortical gray matter nuclei; combined anatomical and functional parcellation of regions that tend to co-activate during resting state, as implemented in Statistical Parametric Mapping (Tzourio-Mazoyer, N., et al., 2002) and purely functional delineations such as the Crad-200, a constrained spectral clustering of resting state fMRI data into 200 parcels encompassing both cortical and subcortical regions, and a high model order Independent component analysis (ICA), as advocated by HCP investigators. Targeted exploration of connectivity driven by current understanding of the pathophysiology of IvPPA will also be pursued.

We will employ age, years of education, gender, and gray matter (GM) volume as time-invariant covariates to obtain residual variables to determine LFC changes due to stimulation. We will model the LFC as a function of these nuisance regressors, using the following multiple linear regression equation, and retain the residuals as $LFC_{Res}^+(s, t)$ for further analysis:

$$LFC(s, t) = \beta_0 + \beta_1 Age(s) + \beta_2 Edu(s) + \beta_3 GM(s) + \beta_4 Gender(s) + Res(s, g, t)$$

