Study Title: High-Definition Transcranial Direct Current Stimulation (HD-tDCS) in logopenic variant Primary Progressive Aphasia (lvPPA): Effects on Language and Neural Mechanisms.

NCT: NCT03805659

Date of document: July 06, 2023

Statistical Analysis:

- The small sample size in this study precluded group-level statistical analysis.
- Instead focused on a within subject item-level analysis.
- Language performances in each trial period were assessed separately to help control for potential carryover effects and for effects of progressive neurodegeneration.
- The Cochran's Q test was used to determine if there were any differences on a dichotomous variable across the three-trial period timepoints.
- Because the same assessment list/version was used within a given stimulation condition per participant, we coded "right" and "wrong" answers to an individual assessment item as our dichotomous variable.
- If the preliminary Cochran's Q test demonstrated a significant difference ($p<0.05$) between participant responses in a language assessment between two timepoints, a follow-up non-parametric pairwise comparison between the baseline and timepoint list was tested using a McNemar test with a false discovery rate correction (Sheppard et al., 2021; Hung et al., 2017; Tsapkini et al., 2015).
- While the Cochran's Q and post-hoc McNemar test allowed us an objective comparison between timepoints within conditions for each individual participant, we utilized a Wilcoxon-signed rank test to assess participant performance changes between aHD-tDCS and sHD-tDCS (ex: aHD-tDCS T0-T1 percentage change from baseline vs. sHD-tDCS T0-T1 percentage change from baseline). This assessment would allow us a more quantitative direct comparison between treatment conditions on an individual participant (Sheppard et al., 2021). The statistical analyses described were performed using SPSS version 27.0 (IBM, Armonk NY). A p-value of <0.05 was used to describe statistical significance.

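### The stated efficacy criterion is a significant change from baseline with no sham comparator, and neither document makes the SAP's active-versus-sham test decisive

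*Protocol*

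**What the plan says.** The Protocol Summary lists two efficacy assessments. The first is feasibility (consent and completion rates). The second is "Statistically significant differences between baseline and post- tDCS stimulation performance on a series of language metrics". The Endpoints row of the Summary words the primary outcome as a change from baseline, and Protocol section 1.3 does likewise: "Language performance as assessed at baseline and post-stimulation procedure (time frame: 2 weeks". None of the three names sham.

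The design does have a control. The Summary describes a "randomized, double-blind, sham-controlled trial in which stimulation or sham will be administered to 20 subjects over the age of 45 years", in crossover. Training is common to both conditions: Protocol section 5.4.4 says of the trained-task items, "with half of them also practiced (i.e. trained) during all stimulation procedures (either sham or real tDCS". The SAP adds that "the same assessment list/version was used within a given stimulation condition per participant", so the same items are answered again at each timepoint of a period.

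The SAP has two layers of testing. Cochran's Q across three timepoints, followed by McNemar tests against baseline with a false discovery rate correction, "allowed us an objective comparison between timepoints within conditions for each individual participant". A Wilcoxon signed-rank test then compares percentage change from baseline under active stimulation with that under sham. The SAP does not say which layer decides efficacy.

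**The concern.** A baseline-to-post difference under active stimulation combines any stimulation effect with ten sessions of training, familiarity with a repeated list, and disease progression. Only the difference from sham separates the first of these from the rest. If the written criterion is applied as it stands, an improvement due to training or practice can be reported as efficacy, and the sham period need not enter the conclusion. Determining efficacy is the stated primary objective, and the results are meant to supply effect sizes for a later trial. A before/after effect size would carry the training gain forward into that trial's sample size.

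**Working it through.** The documents give no power calculation or expected gain for the efficacy criterion, so there is no figure to reproduce. The check asks how often each rule reports a change when stimulation does nothing.

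**Inputs from the documents (Protocol 5.4.4 and SAP)**
- 80 naming pictures per period.
- 288 reading items over two periods: 288/2 = 144 per period.
- 480 trained-task items over two periods: 480/2 = 240 per period. This pools reading (144) with repetition (192/2 = 96).
- 31 items in the alternative naming test.
- Three timepoints and a 0.05 threshold. Sidedness is not stated; two-sided is assumed.

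**Assumptions**
- 50% correct at baseline; logistic item difficulty with SD 1.5.
- A gain of 4 or 9 points from training or practice, equal in both conditions and kept at the third timepoint.
- False discovery rate control by Benjamini-Hochberg over the two McNemar tests.

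**Item-level procedure, one participant, one period**
1. Q = (k−1)[kΣTⱼ² − (ΣTⱼ)²] / (kΣLᵢ − ΣLᵢ²), with k = 3, Tⱼ the number correct at timepoint j and Lᵢ the number of times item i is correct. Refer Q to chi-square on 2 df.
2. If Q is significant, exact McNemar of each later timepoint against baseline: p = min(1, 2·P[X ≤ min(b, c)]), X ~ Binomial(b + c, ½).
3. Apply the correction and count periods with at least one significant comparison.

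| Items per period | 4-point gain | 9-point gain |
|---|---|---|
| 80 | 8% | 25% |
| 144 | 10% | 44% |
| 240 | 16% | 67% |

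Repeat simulations of this set-up differ by up to about 4 percentage points (for example 21% to 25% at 80 items and 9 points). With 31 items and a 9-point gain the rate is 8%. If the 9-point gain is lost by the third timepoint, the rates at 80, 144 and 240 items are 15%, 28% and 49%. Counting only improvement from T0 to T1, with the gain kept, gives 16%, 32% and 53%.

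**Trial level, 20 subjects.** Let d be the training gain in SDs of the change score, with no stimulation effect. The chance that a two-sided 0.05 t-test on change from baseline shows improvement is 1 − F(t₀.₉₇₅,₁₉), where F is the noncentral t distribution on 19 df with noncentrality d√20. For d = 0, 0.2, 0.3, 0.5 and 0.8 this gives 2.5%, 13%, 25%, 56% and 92%. The paired active-minus-sham contrast, simulated with independent changes in the two conditions, rejects in 5.1%, 5.0% and 5.0% of trials at d = 0, 0.5 and 0.8. The training gain cancels.

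**Unit of the Wilcoxon test.** The SAP says that group-level analysis was precluded and describes this test as a comparison for an individual participant. Each participant has one T0-T1 percentage change per test per condition. Whether the pairs are tests within a participant or participants within a test is not stated. It matters: with five pairs the smallest exact two-sided signed-rank p-value is 2/2⁵ = 0.0625, so significance at 0.05 is out of reach.

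**The case against.** The strongest reply is that the plan as a whole does use sham. The SAP's Wilcoxon test compares change from baseline under active and sham directly, and the SAP presents it as the comparison between conditions. Protocol section 6.3 includes a group-by-time test and section 6.5 an active/sham term. This stands: a reader might infer from the Summary line that the plan contains no sham contrast, and that would be wrong.

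Two further inferences also go too far. Neither document says that a significant result under active with a non-significant one under sham will be read as efficacy, and the SAP does not call Cochran's Q and McNemar its main tests. Nor do the documents show that a gain must occur. The disease is progressive, only half of the reading and repetition items are trained, and naming is not trained at all.

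What the reply does not remove is the missing ranking. The Summary criterion can be met without the Wilcoxon test. The protocol analyses do not close the gap either. In section 6.3, "We will test for group and time main effects", and the time effect includes the training signal. Section 6.2 defines the groups as sequences, "both of which will receive both sham and active tDCS at different treatment phase", while section 6.4 glosses group as sham versus stimulation. The group-by-time test is therefore not clearly an active-versus-sham test, and the SAP sets group-level analysis aside.

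**Conclusion.** The point holds for the efficacy criterion and the outcome wording: as written, a practice or training gain could satisfy them without any stimulation effect. It does not extend to a claim that sham is left out of the analysis. The defect is that the existing sham contrast is not made decisive and its pairing unit is not defined.

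Under no stimulation effect, the within-condition procedure declares a change in about 8% to 25% of periods with 80 items and about 16% to 67% with 240 items, for assumed gains of 4 to 9 points. These figures rest on the assumed gain, the item spread and retention of the gain at the third timepoint, and shorter lists give lower rates. They show direction and range only. The argument itself needs none of them: a before/after difference cannot separate stimulation from training that both conditions receive.

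**What to change.** 1. In the Protocol Summary, restate the language efficacy criterion as the active-minus-sham difference in T0-T1 change, and bring the Endpoints row and section 1.3 into line.
2. In the SAP, state that this contrast governs every efficacy statement. Either keep the Wilcoxon test and define its pairs, or use an item-level test of condition by time.
3. Label the within-condition Cochran's Q and McNemar results as descriptive.

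The data for this are already in the plan, so the cost is wording, plus one further analysis if the item-level test is chosen. Fewer results will be available to report as significant. The SAP is written in the past tense; if results are already known, date the change and mark it as made after the analysis.

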1. STUDY OBJECTIVES

The logopenic variant of Primary Progressive Aphasia (lvPPA) is an untreatable neurodegenerative disorder that is often referred to as the 'language form' of Alzheimer's Disease (AD). Transcranial Direct Current Stimulation (tDCS) has emerged as a safe and potentially effective tool that appears to enhance language production when delivered during language training (Tippet et al., 2015). This technology provides a critical opportunity to conduct disease intervention. In this study, we **will test our hypothesis that High-Definition tDCS (HD-tDCS) will improve performance on language tasks by increasing functional connectivity and by regulating abnormal neuronal oscillatory patterns.** The rationale for this project is that a determination of the therapeutic efficacy and the associated neural mechanisms of HD-tDCS in lvPPA is likely to offer a scientific framework whereby new stimulation parameters, conditions, and target sites can be deciphered.

1.1. Justification of Selecting lvPPA Subjects for HD-tDCS Treatment

The sparse number of studies done so far presuppose a conceptual framework predicated on the idea that because of relatively widespread neurodegeneration, these patients do not remap language functions to novel networks, but that instead they continue to use pre-existing neural areas with declining efficiency (Rogalski et al., 2011). This stands in contrast to the working models for post-stroke aphasia recovery where the assumption is that patients will engage in the recruitment of unaffected brain areas as an important compensatory mechanism (Abel et al., 2015). The aforementioned 'neurodegeneration' model would suggest that in the case of lvPPA an appropriate neuromodulation approach would lead to the tailored and narrow stimulation of disease-specific affected brain regions. Notwithstanding the biological plausibility of this model, all the published studies on lvPPA and other PPA subtypes have used conventional tDCS montages, a method incapable of focally targeting specific brain regions. High-Definition tDCS (HD-tDCS) on the other hand, is a recently developed system that allows for more focal stimulation based on increased current focality and intensity (Villamar et al., 2013). What remains lacking is knowledge of the therapeutic efficacy and neural mechanisms of HD-tDCS when used in lvPPA. There is, therefore, a critical need to evaluate the effects on language performance and the underlying neural mechanisms of active HD-tDCS aimed at the left posterior temporo-parietal cortex (TPC), the most consistent neural correlate of this condition (Gorno-Tempini et al., 2011). Without such information the promise of disease-specific and personalized tDCS procedures for the treatment of this neurodegenerative aphasia will likely remain limited.

